#### **EXPECTED RESULTS:**

In this study, it is expected that in the patients who underwent elective surgery, the markers of glycocalyx damage will increase their values in the postoperative laboratory tests compared to the values of the baseline (control) laboratory tests. It is equally expected that in patients undergoing urgent surgery, generally in clinical states of occlusion, perforation or sepsis, with activation of the inflammatory response, dehydration with decreased oncotic pressure and generation of tissue edema and third space, the markers of damage of glycocalyx are already elevated in the baseline analysis, with a maintenance or greater elevation of its values in the postoperative period. Likewise, a correlation would be expected between glycocalyx damage markers and other markers involved in the inflammatory response, such as leukocytes, C-reactive protein, procalcitonin, and lactate; as well as with associated patient comorbidities that lead to endothelial degeneration, such as high blood pressure, obesity, diabetes, atherosclerosis, etc. If the results of this study were as expected, glycocalyx damage markers (Heparan sulfate and Syndecan-1) could be used together with other inflammatory markers (CRP, procalcitonin, etc.) and be very useful in postoperative follow-up. of surgical patients, being able to anticipate possible postoperative complications. However, if elevations in glycocalyx markers were not observed in the perioperative period, it could be due to a lack of the number of Time-course determinations; that is to say, that an elevation of markers did occur, but we would not have detected it in the measurement times; or a larger

study population might also be needed. In either case, the study could be completed in subsequent research projects.

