### **Secondary Objectives:**

- To analyze a possible correlation of the glycocalix damage markers with other analytical parameters (PCR, procalcitonin, lactate, complete blood count, coagulation and basic biochemistry).
- To analyze the possible relationship of glycocalyx damage markers with different parameters depending on the patient (age, sex and associated comorbidities) and the surgical intervention (surgical time, approach, type of surgery...).
- To analyze other clinical parameters that may indicate a possible postoperative complication and their relationship with markers of endothelial glycocalyx damage will also be studied.

**METHODOLOGY DESIGN:** The present work is about a clinical, prospective, observational, and longitudinal study of single center groups (Hospital Lluís Alcanyís, Xàtiva). Always after the approval of the Research Ethics Committee of said Hospital.

**STUDY POPULATION:** The study population (value of n) has been calculated on a population of 100 patients who will undergo surgery approximately one year. With a confidence level of 95% and a margin of error of 5%, a sample size of 80 patients has been calculated. These 80 patients will be of legal age, men and women, undergoing elective or emergency colorectal surgery (right hemicolectomy, extended right hemicolectomy, left hemicolectomy, sigmoidectomy, anterior resection of the rectum or abdominoperineal amputation).

**CHOICE OF PATIENTS AND INFORMED CONSENT:** The selection of patients and the drafting of the informed consent documents will be carried out in a reasoned manner as established in article 32 of the Declaration of Helsinki and in article 58.2 of the Research Law. Biomedical. It should be considered taking into account the Declaration of Helsinki of the World Medical Association in its latest revision. And according to its latest version of the Helsinki Declaration of Fortaleza (Brazil) October

2013. Patients will be included in the study upon preoperative hospital admission, after verifying compliance with the inclusion criteria. To participate, it will be necessary to sign the informed consent.

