#### **METHOD:**

Blood samples will be drawn from an intravenous line, in BD Vacutainer® LH PST™ II tubes with lithium heparin at different times: 1st) basal time (preoperative), at hospital admission; 2nd) 2 hours after the end of the surgery, 3rd) 6 hours after the end of the surgery, 4th) 24 hours after the end of the surgery and 5th) 48 hours after the surgery. The blood samples will be centrifuged at 3000 rpm/12 min and the supernatants will be collected and stored at -80°C until the determination of the markers. Plasma levels of Syndecan-1 and Heparan Sulfate will be determined by ELISA (Enzyme-Linked Immunosorbent Assay), PCR (C-reactive protein), procalcitonin, lactate, blood count, renal function, basic coagulation and general biochemistry techniques. The blood samples will be drawn by the nursing team of the general surgery hospitalization ward, and will be transported to the laboratory by the auxiliary staff of said hospitalization ward. The laboratory staff will be in charge of centrifuging the samples and storing the supernatants in the pertinent conditions mentioned above. Later, when all the samples have been collected, the determination of the markers will be carried out, and the result will be displayed through the Orion clinic computer program or in paper format, which will be delivered to me personally. In addition, all the usual anesthetic, surgical and

postoperative care protocols of the Institution (General and Digestive Surgery Department. Lluís Alcanyís Hospital) will be maintained for these patients.

**STATISTICAL ANALYSIS PLAN (SAP):** Continuous data are expressed as mean  $\pm$  standard deviation. The normality of the data obtained was determined with the Kolmogorov-Smirnov and Shapiro-Wilk tests. Differences between baseline values and different moments after the "time course" of plasma levels of glycocalyx damage markers and other parameters will be analyzed by one-way analysis of variance (ANOVA). Data sets in which F is significant will be examined for multiple comparisons by Tukey's test. The Pearson correlation coefficient (r) will be calculated between the values of the EG damage markers and other parameters. The possible differences between the different population subgroups will be examined with the Student's t-test.  $P < 0.05$  will be considered statistically significant. All statistical calculations will be performed using the SPSS program.

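### The planned Pearson correlations name no unit of analysis for data sampled up to five times per patient; if all values are pooled, the 5% test rejects about 9–25% of the time at assumed ICCs of 0.3–0.7

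*Combined protocol and SAP*

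**What the plan says.** The METHOD section schedules five blood samples per patient: one before surgery, then 2, 6, 24 and 48 hours after it. The SAP paragraph in that section follows both sides of the later correlation over time: "plasma levels of glycocalyx damage markers and other parameters will be analyzed by one-way analysis of variance (ANOVA").

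On correlation it has one sentence: "The Pearson correlation coefficient (r) will be calculated between the values of the EG damage markers and other parameters". The threshold is P < 0.05, which "will be considered statistically significant. All statistical calculations will be performed using the SPSS program".

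The correlation serves the first secondary objective, "To analyze a possible correlation of the glycocalix damage markers with other analytical parameters". It also serves the continuous items, such as age and surgical time, in the second: "To analyze the possible relationship of glycocalyx damage markers with different parameters depending on the patient". Categorical subgroups go to the t-test and are outside this point. EXPECTED RESULTS says that "a correlation would be expected between glycocalyx damage markers and other markers involved in the inflammatory response".

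No section says whether r is computed at one time point, at each time point, on a per-patient summary, or on all values together.

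**The concern.** Pearson's test assumes independent pairs. Five pairs from one patient are not independent if both variables tend to run high or low in that patient. The plan gives no sign that this dependence will be handled: the one-way ANOVA named for the same repeated data has no patient term either.

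A pooled r also mixes three things: whether patients with high markers have high laboratory values, whether the two move together within a patient, and whether both simply change after surgery. EXPECTED RESULTS links the hoped-for clinical use, following patients and anticipating complications, to these markers alongside the inflammatory ones. A significant r that came from repeated sampling or a common surgical course could be misread as support for that use.

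**Working it through.** **Inputs from the documents.** 80 patients (STUDY POPULATION); m = 5 samples each (METHOD); threshold 0.05 (SAP), taken as two-sided because sidedness is not stated. **Assumed:** the ICC of each variable, since the documents give none.

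**The plan's own figure.** With z = 1.96, margin 0.05 and an assumed proportion of 0.5, n0 = 1.96² × 0.25 / 0.05² = 384.1. The finite-population correction for 100 patients gives 384.1 / (1 + 383.1/100) = 79.5, so 80. The stated size is reproduced. It is a calculation for estimating a proportion and does not settle how r is computed.

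**Pooled r, no true association, no change over time.** If samples within a patient are equally correlated, the variance of r is multiplied by 1 + (m − 1) × ICCx × ICCy. The true rejection rate is 2 × (1 − Φ(1.96 / √inflation)), and 400 / inflation is the equivalent number of independent pairs.

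| ICC (both variables) | Inflation | Equivalent pairs | Rejection, formula | Rejection, simulated |
|---|---|---|---|---|
| 0.3 | 1 + 4 × 0.09 = 1.36 | 294 | 9.3% | 9.3% |
| 0.5 | 1 + 4 × 0.25 = 2.00 | 200 | 16.6% | 16.4% |
| 0.7 | 1 + 4 × 0.49 = 2.96 | 135 | 25.5% | 25.7% |

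The simulations used 20,000 trials per setting. At 0.1 in both variables, inflation is 1.04 and rejection 5.5%. For unequal ICCs, 0.3 with 0.7 gives 14.8% and 0.1 with 0.7 gives 8.3%. If either ICC is zero there is no inflation (simulated 4.9% for 0.7 with 0).

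**Pooled r with a shared change after surgery.** Suppose both variables rise by d SD at all four postoperative times and are otherwise unrelated. One sample in five is preoperative, so the step has variance 0.2 × 0.8 × d² = 0.16d². The expected pooled r is 0.16d² / (1 + 0.16d²):

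- d = 0.5: 0.04 / 1.04 = 0.038
- d = 1: 0.16 / 1.16 = 0.138

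For ICCs of 0.3–0.7, simulated rejection is 16–28% and 72–78% respectively. These are not pure type I error rates, because the pooled r is truly non-zero. It describes the common time course, not a patient-level link.

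**One value per patient.** At a single time point with n = 80, simulated rejection is 4.8–5.2%, the nominal level.

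**Elective/emergency mix.** If only the marker is raised by 1 SD in emergency patients, rejection stays at 5.2% (20% emergency) and 5.0% (40%); both shares are assumed. If both variables are raised by 1 SD, a real marginal correlation of p(1 − p) / (1 + p(1 − p)) arises:

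- p = 0.2: 0.16 / 1.16 = 0.138
- p = 0.4: 0.24 / 1.24 = 0.194

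By Fisher's z, with standard error 1/√77, the power to detect these with 80 patients is 23% and 41%.

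**The case against.** **Pooling is not stated.** This stands. The sentence can be read as pooling, but also as one r per time point or per summary, and those keep the 5% level for each test. A reader might infer that the plan has an error rate of 9–25%. The documents do not support that as a fact: it needs pooling and ICCs of 0.3–0.7 in both variables. What remains is that the plan leaves open a choice on which the validity of the p-value depends, and the ANOVA gives no reason to expect the dependence to be handled.

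**The elective/emergency mix.** The study enrols patients "undergoing elective or emergency colorectal surgery", and expects markers already raised at baseline in urgent cases, "with a maintenance or greater elevation of its values in the postoperative period". A reader might infer that even one value per patient gives an invalid test unless urgency is adjusted for. That goes too far. Both variables must differ by urgency, and the plan makes no such statement for age or surgical time. Where both do differ, the marginal correlation is real and the 23% and 41% above are power, not false positives. The mix affects interpretation, not the test's level.

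**Adjustment may remove the signal sought.** This also stands. The plan attributes the raised markers in urgent cases partly to inflammation, so urgency may carry some of the hypothesised link. Nothing in the objectives asks for correlation conditional on urgency, so adjustment should not be the only analysis.

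**Repeated-measures correlation has its own assumption.** It takes samples to be equally correlated, which is doubtful for unevenly spaced times. Under assumed AR(1) correlation of 0.3–0.7 it rejected 6.1–10.4%, against 6.6–19.0% for pooling and 5.5–6.2% with patient-clustered standard errors. The fix therefore allows the clustered alternative.

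**Conclusion.** The concern holds as an unspecified unit of analysis for repeated data, with no patient or time effect. The omission is certain; its size is conditional. With all 400 pairs treated as independent, the nominal 5% test rejects about 9% / 17% / 25% at ICC 0.3 / 0.5 / 0.7 in both variables, and the inflation disappears as either ICC approaches zero. A shared postoperative change adds a pooled r with no patient-level meaning.

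This should be corrected because a clearly better specification is available at little cost. It affects secondary correlations in an observational study. A reader should not extend it to the primary objective, which is to estimate marker levels over time and does not use r.

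**What to change.** Replace the correlation sentence in the SAP with:

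> Values from different times are not pooled as independent. For laboratory parameters measured at the same times as the markers, within-patient association is estimated with patient and categorical time in the model (repeated-measures correlation, or a regression with patient-clustered standard errors if equal correlation between samples is doubtful), with 95% CI. For between-patient association, and for continuous parameters fixed within a patient (such as age and surgical time), each patient contributes one value per variable (a pre-named time point or the mean of the samples), and r is reported with 95% CI. These correlations are exploratory and the number tested is reported.

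Correlations adjusted for or stratified by urgency, including a time-by-urgency term in the within-patient model, are optional sensitivity analyses beside the unadjusted ones. They help to show how much of an association follows the elective/emergency mix.

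**Cost.** SAP wording and slightly more analysis; no new data. ANCOVA for the repeated-measures correlation can be run in the software already named. The likely downside is fewer nominally significant correlations, and within-patient and between-patient association become two separate results. METHOD has the marker assays run after all samples are collected, so if that step is still ahead, the rule can be fixed before any marker value is seen.

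### One unstratified Pearson r across elective and emergency patients includes the difference between the two groups, so it cannot by itself show that a glycocalyx marker tracks inflammation among patients of the same surgical urgency

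*Combined protocol and SAP*

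**What the plan says.** The SAP paragraph gives correlation one sentence: "The Pearson correlation coefficient (r) will be calculated between the values of the EG damage markers and other parameters". It names no stratification, adjustment or sampling time. The sentence serves the first secondary objective: "To analyze a possible correlation of the glycocalix damage markers with other analytical parameters", with CRP, procalcitonin and lactate among the parameters listed.

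The Study Population paragraph puts both kinds of surgery in one cohort: "These 80 patients will be of legal age, men and women, undergoing elective or emergency colorectal surgery". The split between them is not given.

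Expected Results predicts how urgent patients will differ. They are described as "generally in clinical states of occlusion, perforation or sepsis, with activation of the inflammatory response", and in them "the markers of damage of glycocalyx are already elevated in the baseline analysis", with the level maintained or rising further after surgery. The same section expects the glycocalyx markers to correlate with leukocytes, CRP, procalcitonin and lactate. It suggests that, if the results turn out as expected, the markers could be used alongside CRP and procalcitonin in postoperative follow-up.

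The only subgroup method in the SAP is Student's t-test. It compares means and does not change how r is computed.

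**The concern.** The SAP does not say that patients are pooled, but a single r with no stratum in a mixed cohort is most plainly read that way. By the study's own expectation, urgent patients sit higher on both axes of the scatter plot: the glycocalyx marker and the inflammatory marker. Two clouds of points offset in the same direction give a positive overall r even if each cloud is flat.

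At stake is the reading of the first secondary objective. A significant r could be reported as evidence that syndecan-1 or heparan sulfate follows inflammation from patient to patient, when part or all of it reflects emergency cases differing from elective ones, which the clinician already knows. The problem remains with one value per patient at one time point, so it is separate from how the five repeated samples are handled.

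**Working it through.** **The plan's own figure.** There is none for the correlation. The sample size reproduces as a finite-population formula for a proportion, with p = 0.5 assumed: n = 100 × 1.96² × 0.25 / (0.05² × 99 + 1.96² × 0.25) = 96.04 / 1.2079 = 79.5, rounded up to 80. It does not bear on the precision of r, but it fixes n for what follows.

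**Inputs.**
- From the documents: n = 80; significance at P < 0.05; the direction of the urgent/elective difference on both sides.
- Assumed, because the documents are silent: a two-sided test; urgent share p from 15% to 35%; urgent patients higher by d within-group SDs on both variables, d from 0.5 to 2; zero correlation inside each group.

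**Pooled correlation.** The covariance over the whole cohort is p(1−p)d² and each variance is 1 + p(1−p)d², so

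r = p(1−p)d² / (1 + p(1−p)d²).

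At p = 0.25, p(1−p) = 0.1875:
- d = 1: 0.1875 / 1.1875 = 0.16
- d = 1.5: 0.4219 / 1.4219 = 0.30
- d = 2: 0.75 / 1.75 = 0.43

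**Threshold.** At n = 80 the two-sided 5% critical value is |r| = t/√(78 + t²) = 0.220, where t is the 97.5% point on 78 degrees of freedom.

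**Share of simulated studies with a significant pooled r** (4,000 per setting; repeat simulations agree to within about two percentage points):

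| Urgent share | d = 1 | d = 1.5 | d = 2 |
|---|---|---|---|
| 15% | 17% | 53% | 91% |
| 25% | 30% | 80% | 99% |
| 35% | 37% | 91% | 99.9% |

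At d = 0.5 the share is about 6–8%.

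**Sensitivity.**
- Only one of the two variables differs between groups (30% urgent, d = 1): 4.8–5.0%. The effect needs a difference on both sides.
- Unequal shifts of 1 and 2 SD at 25% urgent: r = 0.1875 × 1 × 2 / √(1.1875 × 1.75) = 0.26, significant in 67%. Equal shifts are not required.

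**Partial correlation given urgency.** With zero within-group correlation it is significant in 4.8–5.3% of studies in every setting tried (urgent share 10–50%, d from 0 to 2).

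**The opposite case.** Suppose a true within-group correlation of 0.3, with urgent patients raised on the marker only through inflammation. At 25% urgent and d = 1.5, pooled r averages 0.35 and is significant in 90% of studies; partial r averages 0.30 and is significant in 78%. Over 15–35% urgent and d from 1 to 2, power falls from 82–96% to about 77–79%.

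**The case against.** The strongest reply is that pooled r is not wrong. It estimates the correlation in the enrolled population, and under the assumptions above that correlation is not zero. A reader might infer from the table that a 5% error rate is inflated to as much as 99.9%. The documents do not support that: the stated objective asks for a correlation in this mixed cohort, so the percentages are rates of detecting a real marginal association. They become errors only when r is taken to describe patients of the same urgency. This part of the objection stands.

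Second, urgency may be partly a proxy for inflammation rather than a nuisance. The Summary describes glycocalyx degradation in sepsis as mediated by inflammatory mechanisms, and Expected Results characterises urgent patients by occlusion, perforation or sepsis. Adjusting then removes genuine inflammatory range and costs power, as the last calculation shows. This also stands, and it argues against dropping the pooled r.

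Third, the large shifts have no anchor in the documents. Only a direction is given, entry is limited to ASA III or below, and the explicit statement about raised markers concerns baseline. Markers are also expected to rise after elective surgery, so the postoperative gap may differ. This limits what can be said about size, but not the mechanism.

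Fourth, the Summary and the SAP both plan subgroup comparisons, so readers may see the urgent/elective difference. That is true, but a comparison of means does not tell them how much of r comes from it.

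**Conclusion.** The point holds as an interpretive gap with an inexpensive remedy. The planned r combines the elective/urgent difference with any link inside each group, and the plan offers nothing to tell them apart. If urgent patients are higher on both variables, a significant r can arise with no within-group link. The effect is negligible at d = 0.5, moderate at d = 1 and large from d = 1.5 over the urgent shares considered; it is absent if only one variable differs. These sizes rest on an assumed urgent share, assumed shifts and zero within-group correlation.

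A reader might go further and conclude that pooled r will be significant for CRP, procalcitonin, lactate and leukocytes, and will show only that emergencies differ. The documents do not support this. They give no shift size, at d = 1 or below pooled r would usually not be significant, and the within-group correlation is the unknown the study sets out to examine. Nor does the suggested clinical use rest on these correlations alone: it is conditional and follows several other expectations. The primary objective is not affected.

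**What to change.** In the SAP, keep the pooled Pearson r as the description of the whole cohort. At each sampling time, also report:
1. the partial correlation adjusted for elective versus urgent surgery;
2. r within elective patients and r within urgent patients, each with its number of patients.

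State that any claim that a marker tracks inflammation beyond the elective/urgent contrast will rest on the adjusted and within-group values. Giving all three at every sampling time also shows whether the gap expected at baseline persists after surgery.

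**Cost.** A sentence or two in the SAP and a standard SPSS procedure. Urgency is known for every patient, so no new data are needed. Adjustment uses one degree of freedom: where the groups do not differ, power for a true r of 0.3 was 78% adjusted against 79% unadjusted. The downsides are a little more analysis, an imprecise r in urgent patients alone, and an adjusted r that is smaller and has less power if urgency acts through inflammation.

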**Data: 1/2/2022**

**SUMMARY:** The glycocalyx is a layer of macromolecules that covers the luminal surface of the endothelium, playing an important role in vascular homeostasis. Several studies have shown that in conditions of sepsis there is a degradation of the glycocalyx mediated by inflammatory mechanisms, releasing its components into the bloodstream. These glycocalyx fragments can be measured in blood plasma, showing a correlation between these markers and organ dysfunction, severity and mortality in sepsis situations. However, despite the great interest in glycocalyx biomarkers, their values in patients undergoing colorectal surgery are not well known. Therefore, verifying whether plasma levels of glycocalyx damage markers increase in the perioperative period of colorectal surgery is of great interest at the pathophysiological and clinical level, since the correlation of these markers with postoperative clinical evolution is unknown. In this study we want to determine the plasma levels of Heparan-sulphate and Syndecan-1, two of the most important constituents of the glycocalyx, and perform several measurements to form a "time course" of the plasma levels of these markers, in order to compare the different subgroups of patients undergoing colorectal surgery based on their clinical and surgical characteristics.

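### The time-course ANOVA states no patient term, and the subgroup t-test states neither a time point nor whether level or change is compared

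*Combined protocol and SAP*

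**What the plan says.** All references are to the combined protocol and SAP.

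- **SUMMARY.** The markers are measured repeatedly "in order to compare the different subgroups of patients undergoing colorectal surgery based on their clinical and surgical characteristics".
- **EXPECTED RESULTS.** In elective patients the markers should rise after surgery "compared to the values of the baseline (control) laboratory tests". For urgent patients the expectation at the first sample is that "the markers of damage of glycocalyx are already elevated in the baseline analysis". Their later samples are then expected to stay at that level or climb further.
- **OBJECTIVES.** The primary objective is to estimate the two markers over the perioperative period. The secondary objectives add their relation to patient factors and to features of the operation, including its type. STUDY POPULATION lists six operations and admits both elective and emergency cases.
- **METHOD.** Each patient is sampled five times: before surgery, then at 2, 6, 24 and 48 hours after it.
- **STATISTICAL ANALYSIS PLAN (SAP).** For time, differences from baseline in "plasma levels of glycocalyx damage markers and other parameters will be analyzed by one-way analysis of variance (ANOVA"), followed by Tukey's test if F is significant. For subgroups: "The possible differences between the different population subgroups will be examined with the Student's t-test". On distribution: "The normality of the data obtained was determined with the Kolmogorov-Smirnov and Shapiro-Wilk tests". No action is given if normality fails.

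The SAP states no patient term, group term or time-by-group term. For the t-test it states no time point, no choice of level or change, and no scale. The only F test it mentions is the one for time.

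**The concern.** There are three gaps.

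1. **Time test.** Five samples from one patient are correlated. An ANOVA without a patient term leaves the between-patient variation in the error term, so its error bars and Tukey comparisons do not fit the design.
2. **Subgroup t-test.** The plan itself expects unequal baselines. A t-test on postoperative levels then answers a different question from a t-test on change. A persisting baseline gap could be read as a different response to surgery, or a real difference in response could be missed. A baseline t-test would serve the expected baseline gap and a change t-test would serve the course, but the plan commits to neither.
3. **Factors with more than two levels.** A two-sample t-test gives no overall test for a factor such as type of operation.

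**Working it through.** **The plan's own figure.** The sample size reproduces as a finite-population calculation for a proportion, with p = 0.5 assumed:
n = N z² p(1-p) / [e²(N-1) + z² p(1-p)] = 100 × 0.9604 / (0.0025 × 99 + 0.9604) = 96.04 / 1.2079 = 79.5, rounded up to 80.
This is a precision figure for a proportion. It says nothing about power for marker levels, change or subgroups.

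**Inputs.** From the documents: 80 patients, five times, six operations, P < 0.05. Assumed, because the documents give none: within-patient correlation rho 0.3-0.7 with equal correlation between all times, SD 1, normal data, a rise that is constant over the four postoperative times, and 12, 20 or 32 urgent patients. Simulations used 6,000 to 20,000 studies per setting.

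**1. Time test.** Without a patient term the error mean square estimates 1. The correct one estimates 1 - rho. At rho 0.5 it is therefore 1/(1 - 0.5) = 2 times too large. Rejection rates, independent-groups ANOVA v repeated measures:

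| rho | no change | 0.3 SD rise | 0.5 SD rise |
|---|---|---|---|
| 0.3 | 0.9% v 5% | 37% v 62% | 92% v 98% |
| 0.5 | 0.1% v 5% | 28% v 77% | 94% v 99.8% |
| 0.7 | about 0% v 5% | 18% v 95% | 96% v 100% |

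**2. Level or change** (1 SD baseline gap, rho 0.5, tests at 24 h). For the level test, SE = √(1/n₁ + 1/n₂). With 20 urgent and 60 elective patients SE = 0.258, so a 1 SD gap lies 1/0.258 = 3.9 standard errors from zero. At rho 0.5 the variance of change is 2(1 - 0.5) = 1, so the change test has the same SE. Rejection rates with 12 / 20 / 32 urgent patients:

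| Truth | Level t-test | Change t-test | Time × urgency |
|---|---|---|---|
| Same course in both groups | 88 / 97 / 99% | 5 / 5 / 5% | 5 / 5 / 5% |
| Elective +1 SD, urgent flat (chosen so that levels meet) | 5 / 5 / 5% | 88 / 97 / 99% | 91 / 99 / 99.7% |

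Change and interaction behave alike. What matters is level against change.

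**3. More than two levels.** Six operations give 6 × 5 / 2 = 15 pairs. If all were compared by t-test and none differed, about 36% of studies would show at least one p < 0.05 (simulated; the tests share groups, so the independence figure 1 - 0.95¹⁵ = 54% is too high).

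**4. Scale.** When baselines differ, an interaction depends on the scale. With identical courses on the log scale (1 SD gap, 1 SD rise, assumed log-SD 0.4-0.8), the interaction rejects in 30-67% of studies on raw data and in about 5% on logs. This is an illustration: the documents give no marker distribution.

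**5. What the remedy can deliver.** The 95% CI half-width for change is t × √(2(1 - rho)/n). For 20 urgent patients at rho 0.5 this is 2.093 × √(1/20) = 0.47 SD. For 12 and 32 it is 0.64 and 0.36 SD; for all 80 patients, 0.22 SD. Interaction power for a 0.5 SD difference in rise is about 32-58% over 12-32 urgent patients.

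**The case against.** **One-way may mean one-way repeated measures.** The term counts factors and does not exclude that form. This stands as far as it goes, but the SAP does not say so, and that form would still have no group or time-by-group term.

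**The ANOVA error is conservative.** This also stands. A reader might infer that the time test will produce false claims, or that the primary result is lost. Neither follows: the size falls below 5%, and for rises of 0.5 SD or more the power loss is a few points.

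**The plan does not propose the worst cases.** A reader might take the 36% as the plan's error rate. It is not. The six operations describe eligible surgery, and the SAP does not say that they will be compared pairwise. The figure shows what one reading of the silence would cost.

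**Subgroups are secondary, and comparing courses is partly inferred.** The primary objective is estimation, and the secondary objective on patient and surgical factors can be served by comparing levels. A reader might infer from EXPECTED RESULTS a predicted interaction of known direction. The text allows urgent values either to hold or to rise further, so it fixes no direction. What survives is that the SUMMARY gives subgroup comparison as the purpose of the time course, and the plan does not say what is compared.

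**A mixed model is more than is needed.** For a two-level subgroup, naming the time and choosing level or change would close the gap with the existing t-test. This is accepted in the fix.

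**The interaction figures assume equal correlation between all times.** This is correct. Under a correlation of 0.7 that decays with time, the uncorrected F test has a size of about 7%, so the fix asks for an unstructured covariance or a sphericity correction.

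**Conclusion.** The concern holds as one of under-specification and should be corrected before the markers are analysed. Followed as an independent-groups ANOVA, the time test has a size of 0-1% and loses 25 to 77 percentage points of power for a 0.3 SD rise over rho 0.3-0.7; at 0.5 SD it loses 4 to 6. The subgroup t-test can give opposite answers on the same data according to whether level or change is chosen (88-99% against about 5%), and the plan leaves that choice open. The directions follow from the design and the expected baseline gap. The sizes rest on the assumed gap, correlation, urgent share and constant rise. The subgroup part bears on the summary and secondary aims; the patient term also bears on the time test for the primary objective, whose target is still the overall estimate. Confidence is moderate, because a repeated-measures ANOVA may have been intended.

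**What to change.** - **Model.** For each marker, replace the one-way ANOVA and Tukey with a repeated-measures (mixed) model: patient as the repeated unit; time, urgency and time × urgency; unstructured covariance or a sphericity correction; and multiplicity-adjusted comparisons of each time with baseline.
- **Scale.** Name the log scale now for both markers, report ratios to baseline, and give the raw scale as a sensitivity analysis. Do not make the choice depend on observed skew. It can be fixed before any marker result exists, because "when all the samples have been collected, the determination of the markers will be carried out".
- **Report.** Give the overall time course, the elective/urgent difference at baseline, the change from baseline with 95% CI in each group, and the between-group difference in change.
- **Other two-level subgroups.** For a question about course, use a t-test on change at one named time or on mean postoperative change. For a question about level, use a t-test on level at a named time.
- **More than two levels.** Use one overall test before any pairwise comparison.

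The cost is SAP wording plus one recorded variable: urgency is an enrolment category but is not listed among the data to be collected. No extra samples or patients are needed. The price in precision should be stated: urgent-only intervals will be wide and interaction power low for moderate differences, so subgroup results should be labelled exploratory and reported mainly as estimates with CIs.
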